#### Preliminary work and results

We are one of the first few pediatric hospitals in the United States to implement and describe the development of an LPC program.[6] The LPC program was introduced at Children's Wisconsin (CW) in 2019 and was subsequently initiated in the intensive care units. In October 2021 the program expanded to the rest of the hospital. Our ability to place LPCs in hospitalized children gives us a significant advantage in obtaining high quality evidence regarding LPC use in pediatrics. In our initial test group of 20 successfully placed LPCs, there were no major complications such as VTE or CLABSI (*Table 2*). We did identify a 25% dislodgement rate that we are working to reduce by improving the LPC securement.

LPCs inserted (n)	20
Patients (n)	19
Age (years) median (IQR)	11 (7-15)
Male, n (%)	9 (45%)
Location, n (%)	
Acute Care unit	9 (45%)
Intensive Care unit	11 (55%)
Service, n (%)	
Critical Care	7 (35%)
Gastroenterology	6 (30%)
Hospital Medicine	4 (20%)
Oncology	3 (15%)
Anatomic Site, n (%)	
Cephalic vein	7 (35%)
Basilic vein	12 (60%)
Brachial vein	1 (5%)
Number of insertion attempts, n (%)	
1 attempt	19 (95%)
2 attempts	1 (5%)
Catheter size	
22 gauge	10 (50%)
20 gauge	10 (50%)
PIV insertion attempts prior to LPC.*n (%)	
0 attempts	12 (60%)
1 attempt	4 (20%)
2 attempts	3 (15%)
3 attempts	1(5%)
LPC Duration, days, median (IQR)	5.5 (1-9)
Remained until therapy completion, n (%)	11 (55%)
Complications, n (% )	
Occlusion	2 (10%)
Dislodgement	5 (25%)
Phlebitis	0 (0%)
Venous Thromboembolism	0 (0%)
Central Line Associated Blood Stream	0 (0%)
Infections	

Since the initial pilot of the LPC program, 43 LPCs have been placed at CW as standard of care (up until November 2021, see figure below). All LPCs were placed in the upper extremity (77% in the upper arm); 88% were placed in the PICU. The median (IQR) dwell-time was 6 (3-11) days; 14% remained in for > 14 days (max dwell-time 41 days), 19% for 7-14 days, and 58% for  $\leq$ 7 days. Reason for removal was "no longer medically needed" in 70% (n=30) of the LPCs and complications in 21% (n=9). Most frequent complication was occlusion (n=3) and infiltration (n=2). These complications are similar to those of a peripheral IV. No clots or line infections identified.

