#### E. Design and methods (including experimental design, technical details and laboratory methodology):

#### Study design:

Randomized clinical trial. We propose a parallel group, pragmatic randomized non-inferiority pilot trial design (*arm 1* and *arm 2*) (**Figure 1 below**) assessing the feasibility of a full-scale effectiveness trial comparing PICCs to LPCs for non-central, medium-term vascular access (5-14 days) in pediatrics.

Mixed methods (qualitative and quantitative data) will be used to determine patient/family experience.

**Setting and sample:** This single center pilot study will take place at Children's Wisconsin main hospital in Milwaukee. We plan to use convenience sampling, enrolling Monday through Friday 8-5pm during the one-year timeline.

Inclusion criteria: patients age 2 to 17 years admitted to Children's Wisconsin and requesting placement of a PICC () for: (1) anticipated length of intravenous treatment of 5-14 days, (2) planning peripherally compatible infusates [28] (3) VAD not needed at discharge.

Exclusion criteria: non-English-speaking family, active bacteremia or VTE at site where device would be placed, urgent need of vascular access (within 4 hours), another central venous catheter already in place, device needed for any intervention requiring central access such as medications that cannot be given peripherally OR central monitoring. To be included in the study, the treating attending physician will need to give approval for participation and randomization.

Inclusion/Exclusion criteria for guardian participation in the semi-structured interviews: > 18 years old, English speaking.

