#### Interventions:

After recruitment and consent, patients will be 1:1 randomized to receive:

1. **PICC:** Bard 3fr, 4fr or 6fr; Cook 4fr; or Medcomp 1.9fr and 2.6fr. (type and size to be selected based on interventional radiology standard protocol)

2. LPC: Bard Powerglide 8 cm, 20G and 22G. (size to be selected based on patient size)

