#### / Study-wide (if applicable): N/A

**Describe what are these numbers are based on:** In a prior study, we showed that 139 PICCs over a one-year period could have been avoided at our local hospital as they (1) delivered peripherally-compatible infusates, (2) stayed in for < 14 days and (3) were removed prior to discharge. This is the population that we target for our study. For this pilot trial, we plan to enroll 35 patients in each randomized study group (35 participants in arm 1 and 35 participants in arm 2 of the study). The study is not powered to detect statistical significance, but rather to assess the feasibility of this study protocol for a larger full-scale effectiveness trial and provide baseline estimates for the sample size calculations. With a **sample size of 60 or more** patient subjects, we will be able to estimate a participation rate of 70% (eligible patients agree to enrollment and randomization) within a 95% confidence interval of +/- 12%.

The decision to include up to 70 adult guardians in the semi-structured interview portion was made to reach thematic saturation in qualitative analysis. Selection criteria for the interviews will be based on the number needed to meet qualitative saturation of data. All parents who enroll in the study will be asked to participate in the structured interview until qualitative thematic saturation is met. As such, selection criteria in effect will be based on chronology of participation in the study and number of interviews obtained from participants who agreed.

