#### D. Describe procedures to be employed in analyzing data (including a power analysis):

Quantitative. Study data will be collected using REDCap. Feasibility outcomes will be collected from (1) screening logs maintained by the study team (rate of enrollment, assigned intervention), (2) ease/difficulty of VAD placement (scale 0=worse to 10=best) to determine VAD acceptability, and (3) REDCap datasheet for assessing missed data. Patient demographics (age, gender, race/ethnicity), clinical factors (reason for admission, co-morbidities, reason for PICC/LPC request, therapy to be infused, requesting service, hospital floor), VAD data (VAD type and size placed, insertion site/vessel, sedation, number of attempts, additional VADs), effectiveness data (time-to-removal of VAD, prolonged NPO, number of lab draws from VAD, number of non-VAD blood draws) and complications requiring medical intervention will be collected using the EMR and daily (Monday-Friday) check-ins with the bedside nurse. Procedural pain with non-sedated VAD placement will be assessed in patients age > 5 years by the RC within 24 hours of insertion using the Faces Pain Score (FPS) or the 0-10 pain scale depending on the developmental age of the patient. Patient/parent anxiety and overall experience with VAD placement will be assessed on a 0-10 scale (0= lowest, 10=highest) and using the short State-trait anxiety inventory (STAI) that is validated in children 5 and older.

Descriptive statistics will be used to report feasibility outcomes and explore clinical factors (see above). Cross over rate will be calculated as the proportion of the number of subjects who crosses from the randomized arm/line to a different arm/line. The exact Clopper-Pearson 95% confidence interval will be generated. Time-to-device removal for all reasons will be compared using a t-test. Non-inferiority of LPCs to PICCs will be demonstrated if the 95% confidence interval of the mean difference lies above -1 (non-inferiority margin: 1 day). The remaining outcomes will be compared using Chi-square test or Fisher's exact for categorical variables and t-test or Mann-Whitney-Wilcoxon test for continuous variables. Where necessary for parametric assumptions, appropriate transformations will be employed. Non-parametric tests will be used where parametric assumptions are not satisfied. Logistic regression or general linear model will be performed to control the potential confounders.

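### The t-test that decides non-inferiority ignores planned length of therapy (5-14 days); it is valid, but recording and adjusting for planned days would be a cheap gain in precision

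*Combined protocol and SAP*

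**What the plan says.** Allocation is described in Section 1, part E (Interventions): "After recruitment and consent, patients will be 1:1 randomized to receive" a PICC or an LPC. No stratification factor is named there or elsewhere. The inclusion criteria in the same part, repeated in Section 3, part C, require "anticipated length of intravenous treatment of 5-14 days".

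Section 6, part D sets the comparison: "Time-to-device removal for all reasons will be compared using a t-test". The decision rule follows: "Non-inferiority of LPCs to PICCs will be demonstrated if the 95% confidence interval of the mean difference lies above -1 (non-inferiority margin: 1 day". Later in the same paragraph: "Logistic regression or general linear model will be performed to control the potential confounders". That sentence lists no covariates and is not linked to the non-inferiority interval.

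The data to be collected include "clinical factors (reason for admission, co-morbidities, reason for PICC/LPC request, therapy to be infused, requesting service, hospital floor". Planned number of days of therapy is not in that list. It enters only as an eligibility range, checked on the form that interventional radiology and the attending physician go through before the family is approached (Section 3, parts B and C).

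**The concern.** A device that works comes out when therapy ends. The documents expect this to be the usual course. Section 8, part E puts completion of therapy with a PICC at 80-90%. In the local LPC series (Section 1, part D), 55% of the first 20 stayed to completion, and 70% of the next 43 were removed because they were no longer needed. For many children, removal time therefore reflects the prescribed course, which can differ by up to 14 - 5 = 9 days between two eligible patients, against a margin of 1 day.

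That part of the variation is foreseeable before allocation, at least approximately. Left out of the analysis, it stays in the error term and widens the interval that must lie above -1 day. It also leaves the one trial actually run open to a chance difference between arms in course length that cannot be separated from a device effect. If planned days are never recorded, adjustment is not possible later, and the pilot cannot tell the full-scale trial what SD to expect from an adjusted analysis.

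**Working it through.** **The plan's own figure.** The only sample-size calculation is for a 70% participation rate with 60 patients: 1.96 × √(0.7 × 0.3 / 60) = 0.116, and the exact half-width for 42/60 is 0.122. Both round to the stated ±12%. There is no calculation for removal time.

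**Inputs from the documents.** Sample size: "we plan to enroll 35 patients in each randomized study group". Planned therapy 5-14 days; margin 1 day; 95% interval. PICC failure of 10-20% is the complement of 80-90% completion. LPC failure is taken as 15-45%: the upper end is the complement of 55% completion, and the lower end is an assumption.

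**Assumptions.** The documents give no distribution for planned days. Take whole days 5 to 14 as equally likely, with failure times exponential and the stated failure percentages applying to a 9.5-day course.

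**Step 1: imbalance in planned days.** SD = √(99/12) = 2.87. SE of the arm difference = 2.87 × √(2/35) = 0.687 day. P(difference beyond ±1 day) = 2 × [1 - Φ(1/0.687)] = 14.5%; simulation gives 14.1%. About 7% runs against the LPC. Other shapes at 35 per arm:

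| Planned days | SD | P(beyond ±1 day) |
|---|---|---|
| Symmetric triangular | 1.84 | 2.3% |
| Continuous uniform | 2.60 | 10.7% |
| Whole-day uniform | 2.87 | 14.5% |
| Half at 5, half at 14 | 4.5 | 35% |

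**Step 2: effect on removal time.** The margin applies to removal time, not planned days. Some catheters fail early, so one extra planned day moves mean removal by less than one day: about 0.88 day at PICC/LPC failure of 10/15% and 0.68 day at 20/45%.

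- Slope 0.88: 0.88 × 0.687 = 0.605; 2 × [1 - Φ(1/0.605)] ≈ 10%.
- Slope 0.68: 0.68 × 0.687 = 0.467; 2 × [1 - Φ(1/0.467)] ≈ 3%.

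**Step 3: precision gained by adjustment.** Trials were simulated with removal at the earlier of end of therapy and failure, and analysed with and without planned days as a covariate.

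| Actual versus planned length | Cut in variance of arm difference |
|---|---|
| Equal | 29-58% |
| Differs with SD 3-4 days (assumption) | 14-32% |

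The larger cut in each row is at low failure (10/15%), the smaller at high failure (20/45%). In SE terms, √(1 - 0.29) = 0.84 and √(1 - 0.58) = 0.65 for the first row; √(1 - 0.14) = 0.93 and √(1 - 0.32) = 0.82 for the second.

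**Step 4: effect on the non-inferiority conclusion.** With equal failure in both arms, therapy running as planned and 35 per arm:

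| Failure in each arm | SE, t-test → adjusted (days) | Chance of concluding non-inferiority |
|---|---|---|
| 15% | 0.79 → 0.53 | 25% → 48% |
| 30% | 0.86 → 0.72 | 20% → 30% |
| 45% | 0.89 → 0.81 | 19% → 23% |

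**Step 5: validity.** At a true difference of -1 day the t-test's one-sided error is 0.025 under its normal model, because its SE already contains the variation in planned length.

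**The case against.** The strongest reply is that nothing is wrong with the inference. Randomization makes the unadjusted comparison valid and the SE allows for chance imbalance. That stands. A reader might infer that the plan is biased, or that it will wrongly declare or deny non-inferiority in the share of trials where planned days differ by more than a day. Neither follows: the rule concerns a confidence limit, not a point difference crossing 1 day, and step 5 shows the error rate is held. The 14.5% in step 1 is on the planned-days scale, counts both directions and depends on an assumed shape, so it should not be read as a property of this trial.

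A reader might also infer that planned length accounts for most of the spread in removal time. The documents do not support that. In simulation it explained about 56%, 33% and 19% of the variance at 15%, 30% and 45% failure. In the local series of 43 LPCs, "The median (IQR) dwell-time was 6 (3-11) days", which implies an SD near 8/1.349 = 5.9 if roughly normal; a uniform 5-14 plan would then be about 2.87²/5.93² = 23% of the variance. That series was 88% PICU with 14% beyond 14 days, so it is only a loose guide.

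It is also fair to say that this is a pilot, sized for a participation rate and expressly not powered for the arm comparison, and that a model for confounders is already planned. The first point limits how much the lost precision matters, but the plan still states a formal non-inferiority rule and intends to supply estimates for the full-scale sample size. The second does not close the gap, since the model names no covariate, is not tied to the interval, and planned days are not a listed data item.

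Finally, the unadjusted SD is not wrong for the full-scale calculation; it is the right input if that trial uses an unadjusted analysis. The point is only that the adjusted SD should be available too. If the endpoint were redefined as time to failure or failure-free completion, planned length would matter less than it does for all-cause removal.

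**Conclusion.** The point holds as a loss of precision, not as an error. The comparison that decides non-inferiority leaves out a baseline quantity that bears directly on the outcome, and the plan does not list it for collection. With planned days uniform on 5-14, 35 per arm and PICC/LPC failure between 10/15% and 20/45%, adjustment would reduce the variance of the arm difference by about 29-58% if therapy runs as planned, and by about 14-32% if actual length departs from plan with an SD of 3-4 days. Chance imbalance would shift the removal-time difference by more than 1 day, in either direction, in roughly 3-10% of trials. All these figures rest on assumed distributions, and other shapes would change them. Even with adjustment the trial stays underpowered for a 1-day margin, as its authors acknowledge. This is a worthwhile, inexpensive improvement.

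**What to change.** 1. Add a field for the planned number of days of therapy to the eligibility checklist already completed before randomization, fix the value before allocation, and list it among the data collected in Section 6, part D.
2. Replace the t-test sentence with a linear model for removal time containing arm and planned days, and take the non-inferiority 95% confidence interval from it. The adjusted difference is still in days, so the 1-day margin carries over unchanged.
3. Report both the unadjusted SD and the residual SD from this model for the full-scale sample-size calculation.

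Stratifying the randomization by planned duration is optional once the covariate is in the model.

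The cost is one checklist field and a rewritten analysis sentence. The drawback is that planned length is only an estimate, so the gain may be modest. It cannot be recovered afterwards if the value is not recorded before allocation.

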#### C. Hypothesis/specific aims:

The aims of this pilot, randomized controlled trial are:

*Aim 1:* To assess the feasibility of a full-scale effectiveness trial comparing PICCs to LPCs in hospitalized pediatric patients in need of non-central, medium-term vascular access (5-14 days anticipated need). *Hypothesis:* Feasibility of a full-scale effectiveness trial will be established by demonstrating that > 70% of eligible patients agree to enrollment and randomization, > 80% of randomized patients receive the assigned intervention, > 80% of providers involved find the study acceptable, and < 5% of data are missing.

*Aim 2*: To identify a population in which a LPC is a safe and effective alternative to a PICC for vascular access in hospitalized pediatric patients age > 2 years, in need of non-central, medium-term access. *Hypothesis:* We hypothesize that LPCs are non-inferior to PICCs for delivery of peripherally compatible infusate needed for 5-14 days in hospitalized pediatric patients. We plan to determine the time-to-removal of the vascular access device, both secondary to completion of therapy and secondary to complications. Safety will be assessed by measuring complication rate (e.g., VTE, CLABSI, occlusion, dislodgement, phlebitis). Cross over rate will be closely monitored as well.

*Aim 3:* To engage patients and families as advisors in vascular access device selection. We will describe the patient and family experience with device placement and maintenance as well as perceived patient and parent insertion-related and sedation-related distress.

D. Background, significance, and rationale (including description of preliminary studies and any results):

Many hospitalized children require a vascular access device (VAD) for delivery of life saving interventions such as intravenous fluids and antibiotics.[1] With the broad range of VADs available, and their different profile of complications,[2] it is essential that clinicians have access to rigorous evidence to guide the selection of the most appropriate VAD. Appropriate VAD selection results in treatment efficiency and a decrease in catheter-related complications.[1] The problem is, even the most current and comprehensive guideline for VAD selection published in 2020, the Michigan Appropriateness Guide for Intravenous

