#### Describe what will happen to the subject solely for the purpose of this research study:

The **child participant** will undergo randomization, prospective health data collection, and pain/anxiety assessments related to VAD placement (1 anxiety survey before and 1 repeat anxiety survey with pain rating after VAD placement) solely for the purpose of this study.

The **adult participant (parent/guardian)** would complete anxiety assessments related to their child's VAD placement (1 survey before and 1 repeat survey after placement) and agreement to participate in a semi-structured interview after the VAD is removed. The child participant is welcome to contribute to the semi-structured interview responses with the parent as a child-parent dyad, but the child is not required to do so as part of the study.

The parent and child will be given the first survey to fill out prior to VAD placement. The study team member will distribute and collect the first survey. The repeat survey will be placed in the patient's binder. Following VAD placement (and once child is fully alert if sedation was used during placement), the study team member will either (1) return to distribute the repeat surveys to the family, or if unable (e.g. VAD is placed after business hours) (2) will Voalte the bedside nurse to hand the repeat survey papers to the guardian and child, and store them in the patient's binder upon completion. The study team member will collect the second completed surveys from the families. The study team member will enter the paper survey data into the REDCap database form associated with the participants, and then shred the paper versions. **Describe what is happening per protocol but is considered part of routine care (would happen even if the individual did not participate):** 

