The research coordinator will then approach the subject and guardian to review the IRB-approved informed consent materials and invite them to participate in the randomization trial. After the guardian's written consent and authorization to collect PHI are obtained or declined, the research coordinator will contact the IR and attending physician to notify them of the decision and, if applicable, provide the VAD randomization assignment. For those who participate in the randomization arm, up to 70 families (up to 70 parents/guardians will be enrolled in a structured interview at the end of their hospitalization. This will be discussed with families during the initial informed consent process and if re-visited by the research coordinator for structured interview they will have the option to opt out at that time. Selection criteria for the interviews will be based on the number needed until qualitative thematic saturation is met. As such, selection criteria in effect will be based on chronology of participation in the study and number of interviews obtained from participants who agreed to be interviewed.

Consent and permission/assent to participate in the surveys before and after VAD placement will also be reviewed with the families during the consent discussion and details are included in the consent, assent, and permission forms.

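### The plan collects anxiety scores before and after device placement but does not say how the pre-placement score enters the between-arm analysis, nor that it is taken before the family learns the arm

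*Combined protocol and SAP*

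**What the plan says.** Section 1, under the heading on what happens to the subject solely for research, gives the child "1 anxiety survey before and 1 repeat anxiety survey with pain rating after VAD placement" and the parent or guardian "1 survey before and 1 repeat survey after placement". The timing of the first survey is given only relative to the procedure: "The parent and child will be given the first survey to fill out prior to VAD placement".

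Section 4, item A, has the coordinator contact interventional radiology and the attending physician once consent is settled and, where it applies, "provide the VAD randomization assignment". It does not say when the family hears the assignment, or whether the first survey comes before or after that.

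Section 6, item D (Quantitative), measures patient and parent anxiety on a 0-10 scale and "using the short State-trait anxiety inventory (STAI) that is validated in children 5 and older". The comparison rule covering these scores is the one for continuous outcomes other than time to removal: "t-test or Mann-Whitney-Wilcoxon test for continuous variables". The paragraph ends: "Logistic regression or general linear model will be performed to control the potential confounders". No covariate or outcome is named there. The text also does not say whether the variable tested is the post-placement score or the change from before placement.

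Aim 3 (Section 1, item C) is worded as description: "We will describe the patient and family experience with device placement and maintenance". Sections 3 and 6 say the study is not powered for statistical significance.

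**The concern.** When the same score is measured before and after an intervention, the pre-intervention value is usually the best available predictor of the later one. A two-sample test on the post-placement score ignores it. That costs precision, and it lets part of any chance difference in starting anxiety into the estimated arm difference. With at most 35 per arm, both effects can be noticeable.

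The plan's silence also leaves several analyses open after the data are seen: a t-test or rank test on the post score, a test on the change, or a linear model with or without baseline. These can give different intervals from the same data.

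Timing matters too. Sedation is common for one device and not used for the other, so learning the assignment could itself move anxiety. A first survey completed after disclosure would not be a true baseline, and adjusting for it could remove part of an arm effect on anticipatory anxiety.

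**Working it through.** **The plan's own precision figure.** The plan gives none for anxiety. Its only one is ±12% for a 70% participation rate with 60 subjects. It reproduces: 1.96 × √(0.7 × 0.3 / 60) = 0.116. It does not bear on this point.

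**Inputs from the documents.** 35 per arm (Section 3, item A); anxiety measured before and after placement (Section 1); an unadjusted test as the stated comparison (Section 6, item D).

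**Assumed.** The pre-post correlation r, shown over a range because the documents give neither r nor an SD. Equal SDs at both times and in both arms, and a linear relation. Results are in units of the SD of the post-placement score.

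**95% interval half-widths at 35 per arm.**

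- Post score, unadjusted: t(68) × √(2/35) = 1.995 × 0.239 = 0.477 SD.
- Linear model with the pre-placement score: t(67) × √(2/35) × √(1 − r²) × √(1 + 1/66). The last factor allows for estimating the slope.
- Change score: t(68) × √(2/35) × √(2(1 − r)).

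| r (assumed) | Post score only | Baseline-adjusted | Adjusted vs post only | Change score |
|---|---|---|---|---|
| 0 | 0.477 | 0.481 | about 1% wider | 0.675 |
| 0.3 | 0.477 | 0.459 | 4% narrower | 0.564 |
| 0.5 | 0.477 | 0.416 | 13% narrower | 0.477 |
| 0.7 | 0.477 | 0.343 | 28% narrower | 0.369 |

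The change score uses the first survey but is wider than ignoring it when r is below 0.5. At every r shown, the adjusted model is narrower than the change score.

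**Fewer respondents.** Enrolment starts at age 2, while the plan describes the short STAI as validated from age 5, so the child STAI sample may be below 35 per arm. With 25 per arm (assumed), the half-width is 0.569 SD unadjusted and 0.498 SD adjusted at r = 0.5.

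**Chance imbalance.** With equal SDs, a baseline difference of d shifts the expected post-score difference by r × d. The standard error of d at 35 per arm is √(2/35) = 0.24 SD. A one-standard-error imbalance therefore moves the unadjusted result by 0.3 × 0.24 = 0.07 SD at r = 0.3, 0.12 SD at r = 0.5 and 0.17 SD at r = 0.7.

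**The case against.** The strongest reply is that the plan does not exclude baseline adjustment. Analysis of covariance is a general linear model, the plan announces such a model in the same paragraph, and that sentence lists no covariates for any outcome. The tested variable could also be the change, which uses the first survey. This stands. A reader might infer that the plan throws the pre-placement score away; the documents show only that its use is unspecified. The reply does not close the gap, because nothing commits the analyst to any of these options.

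It is also fair that Aim 3 is descriptive, that the pilot is openly unpowered, and that none of the four feasibility criteria uses anxiety. A reader might infer that an unadjusted comparison would be biased or that a main result is at risk. Neither follows: under randomization, leaving out baseline costs precision and does not bias the comparison. Nor does a chance imbalance carry over in full; it does so in proportion to r.

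Finally, the gain rests on an unknown correlation and is small at r = 0.3. That is true, but the cost at r = 0 is about 1% of interval width. The lack of power is no reason to leave precision unused, since the plan wants the pilot to supply estimates for sizing a larger trial.

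**Conclusion.** The point holds as a gap in specification. The only between-arm comparison the plan spells out for the anxiety scores is unadjusted, and no text gives the pre-placement score a role. On the assumed correlations, naming it as a covariate would narrow the interval at 35 per arm from about 0.48 SD to 0.46 SD (r = 0.3), 0.42 SD (r = 0.5) or 0.34 SD (r = 0.7), with essentially no loss at r = 0. The benefit is confined to precision and protection against chance imbalance in a secondary aim. It also depends on the first survey being a true baseline, which the plan does not secure: that survey is tied to placement and not to disclosure of the assignment.

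**What to change.** In Section 6, item D, state that post-placement STAI and 0-10 anxiety scores, for child and parent separately, will be compared by a linear model with arm and the pre-placement value of the same score as covariates. Report the adjusted mean difference with its 95% confidence interval, using a bootstrap interval if residuals are skewed.

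In Section 1, where the surveys are described, state that the first survey is completed after consent and before the assignment is disclosed to the family. Scores known to have been taken after disclosure should not be used for adjustment. The two changes belong together: adopting the model without the timing rule could adjust for a score the assignment has already affected.

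The cost is one analysis sentence and one survey-timing sentence. The surveys are already planned, so no new data are needed.
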